7.8.2 Rescue medication

Rescue medication use is defined as any initiation of treatment or increase in dose of a medication used to treat JIA (in addition to the IMP) that is considered to impact the efficacy analyses. A study participant requiring rescue medication after first administration of IMP is considered as a treatment failure from that time point forward for the purpose of efficacy analyses. Exception: A study participant initiating rescue medication use after the Week 56 visit will not be considered a treatment failure and the efficacy data will be analyzed as observed without imputation.

A study participant requiring rescue medication may remain on study medication if the benefit/risk assessment of the study participant's continued participation is still favorable based on the Investigator's clinical assessment.

The use of rescue medication should be specifically avoided during the first 4 months (16 weeks) of treatment, if possible.

The following medications are defined as rescue medication in the first 16 weeks of this study:

- Initiation of MTX (if not being used at study entry), or increase of MTX above Baseline.
- Initiation of oral corticosteroids, or increase above Baseline.

The following medications are defined as rescue medication after Week 16:

- Initiation of MTX (if not being used at study entry), and increase of MTX above 15mg/m² per week at any time.
- Initiation of oral corticosteroids, or increase to >10mg or 0.2mg/kg prednisone (or equivalent) per day, whichever is the smaller dose.

The following medications are defined as rescue medication when given at any time during the study:

- Injection of intra-articular (ia) corticosteroids into more than 2 joints at a single time point.
- Injection of intra-articular (ia) corticosteroids into the same joint more frequently than 3 times in a 12-month period.
- Intravenous (iv) corticosteroids (any dose), if not used for stress dosing for the purposes of surgery.
- Intramuscular (im) corticosteroids.

Use of the following medications only results in efficacy data at the next scheduled visit being treated as missing/nonresponse:

- Higher than Baseline dose of NSAIDs and COX-2 inhibitors including PRN use within 72 hours prior to scheduled study visit.
- Higher than Baseline dose of analgesics or opioids including PRN use within 48 hours prior to scheduled study visit.
- Any increase in dose of oral corticosteroids within 7 days prior to scheduled study visit.

All concomitant medications and procedures must be recorded on the CRF. Rescue medication will not be supplied by the Sponsor.

7.8.3 Prohibited concomitant treatments (medications and therapies)

See [Table 6-1](#) for prohibitions prior to study entry. The following are prohibited at any time during the study:

- Nonbiologic DMARDs (other than MTX; see Section [7.8.1](#)) and biologic DMARDs.
- Any experimental (biological or non-biological) therapy (within or outside a clinical study).
- Live and live attenuated vaccinations including, but not limited to, oral polio, chicken pox (varicella), measles-mumps-rubella (MMR), nasal influenza, and rotavirus. No data are available on the response to live vaccinations or the secondary transmission of infection by live vaccines in study participants receiving CZP.

The concomitant use of these must result in the study participant's immediate discontinuation of CZP dosing and the study participant must be withdrawn from the study.

7.9 Lost to follow up

For study participants considered as lost to follow up, the Investigator should make an effort (at least 1 phone call and 1 written message to the participant), and document his/her effort (date and summary of the phone call and copy of the written message in the source documents), to complete the final evaluation.

A participant will be considered lost to follow-up if he or she repeatedly fails to return for scheduled visits and is unable to be contacted by the study site.

The following actions must be taken if a participant fails to return to the clinic for a required study visit:

- The site must attempt to contact the participant and reschedule the missed visit as soon as possible and counsel the participant on the importance of maintaining the assigned visit schedule and ascertain whether or not the participant wishes to and/or should continue in the study.
- Before a participant is deemed lost to follow up, the Investigator or designee must make every effort to regain contact with the participant (at least 1 phone call and 1 written message to the participant), and document his/her effort (date and summary of the phone call and copy of the written message in the source documents), to complete the final evaluation. All results of these evaluations and observations, together with a narrative description of the reason(s) for removing the participant, must be recorded in the source documents. The eCRF must document the primary reason for withdrawal.

Should the participant continue to be unreachable, he/she will be considered to have withdrawn from the study with a primary reason of lost to follow-up documented in the eCRF.

7.10 Enrollment and numbering of study participants

To enroll a study participant, the Investigator must contact the IXRS and provide brief details of the study participant to be enrolled, eg, age, weight, and concomitant MTX use. The Investigator will enter the unique study participant number assigned to each study participant, based on a predefined range of study participant numbers assigned to the Investigator's site. This unique study participant number will be required in all communications between the Investigator (or designee) and the IXRS regarding a particular study participant. The IXRS will allocate container numbers to the study participants based on the unique study participant number during the course of the study. Study participant numbers and container numbers will be tracked via the IXRS and also will be required to be entered into the CRF.

The IXRS will allocate containers of study medication as appropriate to the visit schedule.

8 STUDY PROCEDURES BY VISIT

During the study, the visits will take place in the timeframe as described in the study schedule (Schedule of study assessments, Section 5.2). The acceptable window between all the study visits is +/-3 days **relative to Baseline** (Week 0, Visit 2).

8.1 Visit 1 (Week -4 to 0) Screening

Prior to any study activities and at least 4 days prior to the Baseline Visit (Visit 2), study participants and parent(s)/legal representative, as applicable, will be asked to read and sign an Informed Consent/Assent Form that has been approved by an IRB/IEC and which complies with regulatory requirements. Study participants and parent(s)/legal representative will be given adequate time to consider any information concerning the study given to them by the Investigator or designee. As part of the informed consent procedure, study participants and

parent(s)/legal representative will be given the opportunity to ask the Investigator any questions regarding potential risks and benefits of participation in the study.

Assessments at this visit will include:

- Obtain written informed consent/assent
- Assessment of inclusion/exclusion criteria
- Demographic data including date of birth, gender, and race/ethnicity
- JIA history and prior JIA medication
- Review of general medical and procedure history, concomitant diseases, and previous and concomitant medications
- Vital signs
- Height*
- Weight*
- Physical examination
- TB questionnaire
- Hematology/biochemistry/urinalysis (including hepatitis and HIV testing)
- Reproductive potential and birth control
- Pregnancy (serum) test for postmenarcheal females
- CRP
- Chest radiographic imaging and results must be available at Baseline before first IMP administration unless a chest X-ray or CT scan is available from 2 months prior to Screening.
- TB screening: TST and IGRA for study participants from 2 to 4 years of age (unless the study participant is located in a country with high TST positivity and/or written documentation for BCG vaccination is available) or IGRA (to be performed by the central lab) for study participants from 5 to 17 years of age. Note that the TST may be positive due to BCG vaccination, however, UCB will not permit enrollment of pediatric study participants <5 years old into the study without written approval from a physician with expertise in pediatric TB**
- TB questionnaire (study participant and parent/caregiver)**
- PRINTO/PRCSG standard joint examination
- Physician's Global Assessment of Disease Activity (VAS)
- CHAQ-parent reported
- Parent's Assessment of Arthritis Pain (VAS)
- Parent's Global Assessment of Overall Well-Being (VAS)

- Adverse events
- IXRS contact (to register study participant with unique study participant number)

*Change in height and weight over the last 6 months and over the last year will be collected via parent-/self-report, if not available from medical records.

**For details of TB screening and testing, see Section 10.7.9.

8.2 Visit 2 (Week 0) Baseline

- Assessment of inclusion/exclusion criteria
- Vital signs (within approximately 15 minutes prior to dosing and [pulse and blood pressure only] approximately 30 minutes after dosing)
- Height
- Weight (measurement used to determine CZP dose according to Table 7-1)
- Tanner stages (except growth)
- Physical examination
- TB questionnaire (study participant and parent/caregiver)
- Hematology/biochemistry/urinalysis (only if in the Investigator's opinion there is a change in the study participant's status compared to the Screening Visit, ie, any valid result from hematology, biochemistry, or urinalysis obtained at the Screening Visit will be used as the Baseline value)
- Reproductive potential and birth control
- Pregnancy (urine) test for postmenarcheal females
- CRP
- PRINTO/PRCSG standard joint examination
- Physician's Global Assessment of Disease Activity (VAS)
- CHAQ-parent reported
- Parent's Assessment of Arthritis Pain (VAS)
- Parent's Global Assessment of Overall Well-Being (VAS)
- DMS
- JADAS
- FPS-R for study participants ages 5 to 11 years (at Baseline and daily assessment on Day 1 to Day 7)
- JIA Pain VAS for study participants ages 12 to 17 years; acute and standard versions (both at Baseline and daily assessment of the acute version on Day 1 to Day 7)
- Fatigue Assessment Scale

- Juvenile Arthritis School Attendance and Caregiver Work Productivity Survey
- Concomitant medications and procedures
- Adverse events
- IXRS contact (to receive assigned container number[s])
- CZP plasma concentrations
- Anti-CZP antibodies
- Autoantibodies (ANA antibodies and, if ANA is positive, anti-dsDNA antibodies)
- CZP administration (Injection by site personnel including demonstration for training.)

Documentation of the assessment of all 6 core set measures of PedACR response (PRINTO/PRCSG standard joint examination, Physician's Global Assessment of Disease Activity [VAS], CHAQ-parent reported, Parent's Assessment of Arthritis Pain [VAS], Parent's Global Assessment of Overall Well-Being [VAS] and CRP) **will be submitted to UCB or designee for immediate review of completeness, while the study participant is still on site.**

8.3 Visits 3 and 4 (Weeks 1 and 2)

- Vital signs (within approximately 15 minutes prior to dosing and [pulse and blood pressure only] approximately 30 minutes after dosing)
- Weight (at Week 2 measurement used to reassess CZP dose according to [Table 7-1](#))
- CRP
- PRINTO/PRCSG standard joint examination
- Physician's Global Assessment of Disease Activity (VAS)
- CHAQ-parent reported
- Parent's Assessment of Arthritis Pain (VAS)
- Parent's Global Assessment of Overall Well-Being (VAS)
- Collection of JIA Pain VAS or FPS-R completed on Day 1 to Day 7
- Clinically Inactive Disease
- DMS
- JADAS
- Fatigue Assessment Scale
- Concomitant medications and procedures
- Adverse events
- IXRS contact
- CZP plasma concentrations (Week 1 only)

- Anti-CZP antibodies (Week 1 only)
- CZP administration (Week 2 only. Self/or parent/caregiver-administration under the supervision of the site staff for training.)

8.4 Visits 5 to 10 (Weeks 4, 8, 12, 16, 20, and 24)

- Vital signs (within approximately 15 minutes prior to dosing and [pulse and blood pressure only] approximately 30 minutes after dosing)
- Height (Week 24 only)
- Weight (measurement used to reassess CZP dose according to [Table 7-1](#))
- Tanner stages (except growth; Week 24 only)
- Physical examination
- TB questionnaire (study participant and parent/caregiver) (Weeks 12 and 24 only)
- Hematology/biochemistry/urinalysis
- Reproductive potential and birth control
- Pregnancy (urine) test for postmenarcheal females (Weeks 8, 16, and 24 only)
- CRP
- PRINTO/PRCSG standard joint examination
- Physician's Global Assessment of Disease Activity (VAS)
- CHAQ-parent reported
- Parent's Assessment of Arthritis Pain (VAS)
- Parent's Global Assessment of Overall Well-Being (VAS)
- Clinically Inactive Disease
- Clinical remission on medication (at Week 24 only)
- DMS
- JADAS
- FPS-R for study participants ages 5 to 11 years (Weeks 4, 12, 16, and 24 only)
- JIA Pain VAS (standard version, Weeks 4, 12, 16, and 24 only for study participants ages 12 to 17 years)
- Fatigue Assessment Scale (Weeks 4, 8, 16, and 24 only)
- Juvenile Arthritis School Attendance and Caregiver Work Productivity Survey
- Concomitant medications and procedures
- Adverse events
- IXRS contact (Assignment of all required study medication until next scheduled visit.)

- CZP plasma concentrations (predose at Weeks 4, 12, 16, and 24. Study participants will return to the clinic site for a **postdose CZP plasma sample** approximately **5 to 7 days following the Week 16 visit.**)
- Anti-CZP antibodies (predose at Weeks 4, 12, 16, and 24)
- Autoantibodies (ANA and anti-dsDNA antibodies) (Week 16 only)
- CZP administration (At Week 4, self/parent/caregiver-administration under the supervision of the site staff for training. After Week 4, administration of study medication either by site personnel [for those not performing home-based administration] or self/parent/caregiver-administration under supervision of site personnel to ensure proper injection technique.)

Between scheduled visits (Weeks 6, 10, 14, 18, 22, 26, 28, 30), CZP will be administered at home by the study participant or parent/caregiver or study participants may visit the site for CZP administration by staff personnel.

Documentation of the **Week 24** assessment of all 6 core set measures of PedACR response (PRINTO/PRCSG standard joint examination, Physician's Global Assessment of Disease Activity [VAS], CHAQ-parent reported, Parent's Assessment of Arthritis Pain [VAS], Parent's Global Assessment of Overall Well-Being [VAS], and CRP) **will be submitted to UCB or designee for immediate review of completeness, while the study participant is still on site.**

8.5 Visits 11 and continuing (Week 32 and every 8 weeks thereafter)

For study participants enrolled prior to Protocol Amendment 9, visit frequency changes to every 16 weeks instead of every 8 weeks following implementation of Protocol Amendment 8, provided that compliance is maintained with the CZP dosing schedule using at-home administration.

- Vital signs (within approximately 15 minutes prior to dosing and [pulse and blood pressure only] approximately 30 minutes after dosing)
- Height (Week 48 and every 24 weeks thereafter; for study participants enrolled prior to Protocol Amendment 9, height assessment will be performed every 48 weeks following Protocol Amendment 8)
- Weight (measurement used to reassess CZP dose according to [Table 7-1](#))
- Tanner stages (except growth; for study participants enrolled prior to Protocol Amendment 9, Tanner stages assessment will be performed every 48 weeks following Protocol Amendment 8, and only for those subjects who have not reached Tanner stage V)
- Physical examination
- TB screening once a year (at least every 48 weeks)

- TB questionnaire (study participant and parent/caregiver) (Week 40 and every 16 weeks thereafter)
- Hematology/biochemistry/urinalysis
- Reproductive potential and birth control
- Pregnancy (urine) test for postmenarcheal females
- CRP
- PRINTO/PRCSG standard joint examination
- Physician's Global Assessment of Disease Activity (VAS)
- CHAQ-parent reported
- Parent's Assessment of Arthritis Pain (VAS)
- Parent's Global Assessment of Overall Well-Being (VAS)
- Clinically Inactive Disease
- Clinical remission on medication
- DMS
- JADAS
- FPS-R for study participants ages 5 to 11 years
- JIA Pain VAS (standard version, ages 12 to 17 years)
- Fatigue Assessment Scale
- Juvenile Arthritis School Attendance and Caregiver Work Productivity Survey
- Concomitant medications and procedures
- Adverse events
- IXRS contact (Assignment of all required study medication until next scheduled visit.)
- CZP plasma concentrations (for study participants enrolled following Protocol Amendment 9 only; Weeks 32, 40, and 48 and every 24 weeks thereafter)
- Anti-CZP antibodies (for study participants enrolled following Protocol Amendment 9 only; Weeks 32, 40, and 48 and every 24 weeks thereafter)
- Autoantibodies (ANA and anti-dsDNA antibodies) (Week 48 only)
- CZP administration (Administration of study medication either by site personnel or self/parent/caregiver-administration under supervision of site personnel to ensure properly performed.)

Between scheduled visits (starting at Week 34), CZP will be administered at home by the study participant or parent/caregiver or study participants may visit the site for CZP administration by staff personnel.

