- ^d Pulse, systolic/diastolic blood pressure, and temperature to be measured within approximately 15 minutes prior to dosing and in addition (pulse and blood

Table 5-1 Schedule of study assessments

| Study period | Screening | Baseline | | | | | | | |
|----------------------------------|------------------------|----------|---|---|---|--|--------------------------------|------------------------------------|-------------------------------|
| Week | -4 to 0 ^(a) | 0 | 1 | 2 | 4, 8, 12, 16, (17 ^(u)), 20, 24 | 32 and every 8 weeks thereafter ^(z) | Unsch. Visit ^(b) | Early Disc/ End of Treatment | Final Visit ^(c) |
| Visit (+/-3 days) ^(a) | 1 | 2 | 3 | 4 | 5 to 10 | 11 onwards | | | FV |

pressure only) approximately 30 minutes after dosing.

- ^e Change in height and weight over the last 6 months and over the last year will be collected via parent-/self-report, if not available from medical records.
- ^f Height and Tanner stages to be measured at Week 24 and 48, every 24 weeks thereafter (for study participants enrolled prior to Protocol Amendment 9, Tanner stages assessment will be performed every 48 weeks following Protocol Amendment 8, and only for those subjects who have not reached Tanner stage V) and at Early Discontinuation/End of Treatment.
- ^g From Week 2 onwards, weight measurements will be used to readjust the CZP dose as needed according to [Table 7-1](#).
- ^h Physical examination findings (except joint examination) are recorded in the CRF only at Screening. Subsequent physical examinations are to be recorded in the source documentation and clinically significant findings recorded as AEs.
- ⁱ TB questionnaire to be completed at Weeks 12 and 24 and every 16 weeks thereafter, and Early Discontinuation/End of Treatment. If the Investigator suspects latent TB or active TB, TB testing and/or a chest x-ray should be performed as outlined in [Section 10.7.9](#).
- ^j Hematology/biochemistry/urinalysis will be performed by a central laboratory, except urine dipsticks, which will be done locally at the site. Study participants do not have to be fasting.

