10.7.2 Growth (height and weight)

Height will be recorded at Screening, Baseline, every 24 weeks thereafter (for study participants enrolled prior to Protocol Amendment 9, the height assessment will be performed every 48 weeks following Protocol Amendment 8), and the Early Discontinuation/End of Treatment Visit. Height will be recorded after the shoes have been removed. Height should preferably be measured with a wall-mounted stadiometer.

At Screening, change in height and weight over the last 6 months and over the last year will be collected via parent-/self-report, if not available from medical records.

Weight will be recorded after removal of shoes and heavy clothing. Weight will be measured at Screening, Baseline, and every visit through the Early Discontinuation/End of Treatment Visit, and the Final Visit 12 weeks after the last dose of study medication.

Results of the weight measurement will be used to determine the study participant's CZP dose as specified in [Table 7-1](#).

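### TB questionnaire weeks were not re-anchored when earlier-enrolled participants moved to 16-weekly visits, so one of the two possible visit cycles never meets them; the 48-week height/Tanner rule has no starting week, and height has two conflicting intervals

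*Protocol*

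**What the plan says.** **Visits.** From Week 32 the protocol schedules visits every 8 weeks. For those enrolled before Amendment 9, Section 8.5 states: "visit frequency changes to every 16 weeks instead of every 8 weeks following implementation of Protocol Amendment 8, provided that compliance is maintained" with the at-home dosing schedule. Table 5-1 footnote z repeats the change for on-site dosing, safety sampling and efficacy assessments. Neither place says at which week a participant's 16-weekly cycle starts.

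**TB questionnaire.** Section 8.5 lists "TB questionnaire (study participant and parent/caregiver) (Week 40 and every 16 weeks thereafter". Table 5-1 footnote i gives the same series: "TB questionnaire to be completed at Weeks 12 and 24 and every 16 weeks thereafter, and Early Discontinuation/End of Treatment". Neither makes an exception for earlier-enrolled participants.

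**Height and Tanner stages.** Table 5-1 footnote f sets the base schedule: "Height and Tanner stages to be measured at Week 24 and 48, every 24 weeks thereafter". Its 48-week exception for earlier-enrolled participants names Tanner stages only, and Section 4.3 does the same. Section 8.5 differs on height: "for study participants enrolled prior to Protocol Amendment 9, height assessment will be performed every 48 weeks following Protocol Amendment 8". Section 10.7.2 agrees with 8.5: "the height assessment will be performed every 48 weeks following Protocol Amendment 8". None of these places, nor Section 10.7.3 on Tanner, says which week the 48 weeks are counted from.

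**The concern.** The questionnaire weeks suit an 8-weekly grid, on which each of them is a visit. Once visits are 16 weeks apart, only half of the old grid remains, and which half depends on when the participant switched. Most other schedules affected by the change carry an explicit statement for earlier-enrolled participants: the Faces Pain Scale, the JIA Pain VAS, the fatigue scale, laboratory sampling and Tanner stages. The TB questionnaire does not, which suggests that it was overlooked.

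The questionnaire has a defined role. Under Section 10.7.9.7 any positive answer during the study should trigger further assessment for latent or active TB. The scheduled IGRA test is only about once every 48 weeks. A participant whose visits never coincide with a questionnaire week would, on the written schedule, not be asked the exposure and symptom questions again until treatment ends.

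Height and Tanner stages are safety data with planned summaries (Section 13.3). If sites read the interval differently, the growth series of the earlier-enrolled participants will be measured at unequal intervals for no clinical reason.

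**Working it through.** **Inputs**

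- TB questionnaire: Week 24, then every 16 weeks (footnote i); Week 40, then every 16 weeks (8.5).
- Visits before the change: Week 32, then every 8 weeks (8.5, Table 5-1).
- Visits after the change: every 16 weeks from whichever 8-weekly visit the participant has reached (8.5, footnote z).
- Visit window: 3 days either side, relative to Baseline (Section 8, footnote a).
- Height/Tanner before the change: Weeks 24, 48, 72, 96, 120, ... (footnote f).
- Height/Tanner after the change: 48-weekly for Tanner everywhere; for height 48-weekly or 24-weekly, depending on the section.

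**Step 1: reproduce the stated questionnaire week.** 24 + 16 = 40, so footnote i and Section 8.5 agree. The series is 40, 56, 72, 88, 104, .... Each leaves remainder 8 on division by 16.

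**Step 2: the visit cycles.** The 8-weekly visits 32, 40, 48, 56, ... leave remainders 0, 8, 0, 8, .... From a switch visit at week s, later visits are s + 16k, which keep the remainder of s. There are therefore two cycles:

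- Remainder 8 (for example 56, 72, 88, ...): every later questionnaire week is a visit.
- Remainder 0 (for example 48, 64, 80, ...): no questionnaire week is ever a visit. The nearest one is 8 weeks = 56 days away, and a window of 3 days cannot bridge that.

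This does not depend on how long follow-up lasts.

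**Step 3: height and Tanner.** Because 48 = 3 × 16, a 48-weekly series also keeps its remainder. Counted as 48, 96, 144, ... it has remainder 0; counted as 72, 120, 168, ... it has remainder 8. Both continue the earlier 24-weekly series, and the text does not choose between them. A 24-weekly series alternates between remainders (24 = 16 + 8), so it meets either visit cycle every other time.

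To show how much the reading matters, I assumed twelve possible switch visits, Weeks 56 to 144 in steps of 8, and counted which series never falls on a later visit:

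| Reading of the height/Tanner rule | Loses neither | Loses TB only | Loses height/Tanner only | Loses both |
|---|---|---|---|---|
| 48-weekly, fixed at 48, 96, 144, ... | 0 | 6 | 6 | 0 |
| 48 weeks after the last 24-weekly measurement | 4 | 4 | 2 | 2 |
| 48 weeks from the switch visit | 6 | 6 | 0 | 0 |
| Height 24-weekly (footnote f, Section 4.3) | 6 (half of heights met) | 6 (half of heights met) | 0 | 0 |

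The twelve switch points are an illustration, not an estimate of how participants are distributed. Under all four readings the same six switch visits (64, 80, 96, 112, 128, 144) lose the TB questionnaire, because that result does not involve the height rule.

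**Step 4: height interval.** Set side by side, footnote f and Section 4.3 leave height at 24 weeks for earlier-enrolled participants, while Sections 8.5 and 10.7.2 set it at 48. No calendar assumption is needed to see this conflict.

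**The case against.** The strongest reply is that the questionnaire interval and the new visit interval are both 16 weeks, so a sensible site will simply complete the form at each visit and nothing is lost. TB vigilance does not rest on the form alone either: physical examination is done at every scheduled visit (10.7.4), investigators are told to consider all possible TB sites during it (10.7.9.1), adverse events are solicited at each visit, and IGRA may be repeated at discretion (10.7.9.5). This stands as a limit on the practical harm. It does not remove the fault, because the protocol names weeks and gives earlier-enrolled participants no exception. A site that follows the table literally would not do the questionnaire at any visit on the remainder-0 cycle.

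A reader might also infer that every earlier-enrolled participant must lose either the TB questionnaire or height/Tanner. The documents do not support that. It follows only if height and Tanner are fixed at Weeks 48, 96, 144, and no passage fixes them there. A participant seen at 72, 88, 104, 120, ... with height and Tanner at 72, 120, 168 loses neither. The move to 16-weekly visits is also conditional on dosing compliance, so some participants may remain on 8-weekly visits and be unaffected.

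**Conclusion.** The point holds in three parts. First, the questionnaire weeks never meet the scheduled visits of participants whose 16-weekly cycle runs 48, 64, 80, ...; this follows from the stated weeks alone, read literally, and begins only after the participant has switched. Questionnaire weeks before the switch were ordinary visits and are not lost. Second, the 48-week height/Tanner rule lacks a starting week, so whether it can be met on schedule is undetermined. Third, the height interval for earlier-enrolled participants is contradictory, two places against two.

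The number affected cannot be given. A reader might take the 156 participants planned before Amendment 9 out of 186 in all, or 156/186 = 84%, as the size. That would ignore the split between the two cycles, the compliance condition and those no longer on treatment. It is not even the number enrolled, since Section 1 reports interim results from the first 163. The protocol gives no participant's study week at Amendment 8.

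This should be corrected: it concerns a scheduled TB safety check and a growth safety series, and the repair is cheap. It does not bear on the primary PK or primary safety variables.

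**What to change.** Reconcile Table 5-1 footnotes f, i and z with Sections 4.3, 8.5 and 10.7.2, and carry the result into Section 10.7.3. For participants on the 16-week schedule:

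- state the timing of the TB questionnaire, height and Tanner stages relative to visits that actually take place, so that no participant's cycle can miss them;
- say from which visit the 48-week interval is counted;
- give one height interval in all four places.

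Which intervals apply is for the sponsor to decide; the need here is that the passages agree and can be carried out on the visits scheduled. The cost is wording in three footnotes and a few sections, together with any visit map built from the table. No visits are added.
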